6.6.1.2. Specific MS medical history

Specific complications or symptoms associated with MS are recorded on a specific the eCRF pages 'MS History - Complication or Symptoms (AC-058B301) and ongoing at signature of Informed Consent in AC-058B303' as well as 'MS disease changes'. Complications and symptoms originating from these pages are flagged to be summarized separately. Only specific MS medical history that is ongoing at the start of the extension study will be summarized. The question 'Ongoing at Visit 1 – AC-058B303' (Yes/No) will be used to identify MS medical history ongoing at the start of the extension study. Only records with answer "Yes" will be considered as ongoing at start of the extension.

6.6.2. Analysis of medical history

Medical history ongoing at the start of the extension study will only be summarized for the Extension Analysis Period, by core study treatment and overall, using the EXTS. The number and percentages of subjects who had/have at least one event and had/have each disease/diagnosis (by system organ class [SOC] and preferred term) will be tabulated. SOCs are sorted by descending order of frequency overall. If the frequencies of SOCs are the same, alphabetical order is used. The same rule applies for preferred terms within SOC.

Any additional medical history collected in the extension (not reported in the core study) will be listed only.

Complications or symptoms associated with MS ongoing at the start of the extension study are summarized by study treatment group and overall, by tabulating the number and percentages of subjects who had/have each complication/symptom (by predefined term sorted by descending order of frequency overall).

MS disease changes since entry into the core study will be listed separately (these data are not coded).

All variables including – as applicable – the treatment day relative to study treatment start date of start and end date of diagnosis/disease are presented in a subject data listing.

6.7. Appendix 7 Intervention Compliance

Compliance calculation is not applicable for this study.

6.8. Appendix 8 Adverse Events of Special Interest

The definitions for AESIs are based on the systematic approach using Standardized MedDRA Queries (SMQ). The definitions for AESIs are based on the systematic approach using Standardized MedDRA Queries (SMQ) / MedDRA version 26.0. The following safety areas are addressed by the pre-defined AESIs:

Table 10: AESI

AESI	SMQ	PT		
Bradyarrhythmia occurring post-first dose	Bradyarrhythmias (including conduction defects and disorders of the sinus node function)	Blood pressure ambulatory decreased, Blood pressure decreased, Blood pressure decreased, Blood pressure diastolic decreased, Blood pressure fluctuation, Blood pressure orthostatic decreased, Blood pressure orthostatic decreased, Blood pressure systolic decreased, Bradycardia, Central bradycardia., Chronotropic incompetence, Circulatory collapse, Diastolic hypotension, Electrocardiogram RR interval prolonged, Heart rate decreased, Hypotension, Labile blood pressure, Loss of consciousness, Mean arterial pressure decreased, Orthostatic hypotension, Presyncope, Procedural hypotension, Syncope		
Macular edema		Cystoid macular oedema, Diabetic retinal oedema, Macular cyst, Macular hole, Macular oedema, Macular pseudohole, Macular rupture, Papilloedema, Pseudopapilloedema, Retinal oedema		
Bronchoconstriction	Asthma/bronchospasm (narrow and broad) Interstitial lung disease (narrow and broad)			

Table 10: AESI

AESI	SMQ	PT
Severe liver injury	Hepatic failure, fibrosis and cirrhosis and other liver damage-related conditions (narrow)	
	Hepatitis, non-infectious (narrow)	
Serious opportunistic infections including PML	Opportunistic infections (narrow)	
Skin cancer	Skin neoplasms malignant and unspecified (narrow and broad)	
Non-skin malignancy	Malignant or unspecified tumours (narrow and broad) excluding the PTs included in the SMQ Skin neoplasms malignant and unspecified (narrow and broad)	
Convulsions	Convulsions (narrow)	
Unexpected neurological or psychiatric symptoms/signs (PRES, ADEM, atypical MS relapses)		Acute disseminated encephalomyelitis, Posterior reversible encephalopathy syndrome, Multiple sclerosis relapse

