1.2.3. Treatment period

The treatment period starts with the first dose of study treatment, which defines Day 1 of the extension study. All post-dose assessments of Visit 1 will be conducted during the treatment period.

The treatment period consists of 240 weeks of treatment with ponesimod including a 14-day gradual up-titration beginning on Day 1, followed by daily treatment with 20 mg ponesimod. Treatment will stop before 240 weeks if ponesimod becomes commercially available for the treatment of multiple sclerosis in the subject's country (Treatment may also stop before 240 weeks for subjects prematurely discontinued study treatment due to efficacy or safety or other reasons). The visits during the treatment period will consist of an enrollment visit; three visits at 2 (i.e., 15 days), 4, and 12 weeks after enrollment; and visits every 12 weeks thereafter until the EOT visit. The treatment period may include a study treatment interruption period of variable duration. The permitted maximum duration of the study treatment interruption is 81 weeks for planned pregnancies and 12 weeks for other reasons (if exceeded, then the subject will be prematurely discontinued from the study). During the treatment interruption the subject may follow the planned visit schedule off-treatment with the corresponding assessments with exceptions of assessments that are contra-

indicated due to the subject's condition (e.g., in the event of pregnancy, scheduled MRI assessments will not be performed).

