1.2.3.1. End-of-treatment visit

The EOT visit will take place at Week 240 or at the time ponesimod is commercially available for treatment of MS in the subject's country (whichever occurs first). The EOT visit should preferably take place 1 day after the last dose of study treatment but no later than 14 days after the last dose of study treatment. The EOT visit may take place in case:

- of premature discontinuation of study treatment for subjects meeting the study specific criteria for permanent discontinuation of study treatment;
- the sponsor decides to stop the extension study;
- the subject or the investigator decides to discontinue the study treatment;
- ponesimod is commercially available for the treatment of MS in the subject's country.

In some countries, additional reimbursement negotiations and central formulary approvals will be needed before ponesimod becomes available. In this case, subjects participating in the AC-058B303 study can continue to receive ponesimod until ponesimod is available in their respective country, or for a maximum of 240 weeks. Subjects will get access to the study drug for a maximum of 240 weeks*. If ponesimod becomes available locally before the end of the 240 weeks in the AC-058B303 extension study, then subjects will be considered as having completed the extension study and will be switched to commercially available supply if they wish to continue ponesimod treatment. For these subjects, the switch to commercially available ponesimod should occur at the EOT visit, and commercially available ponesimod may be initiated on the day following last intake of study treatment.

[figure not shown]
*except for subjects in Ukraine where the maximum treatment duration will be 288 weeks (or not later than preplanned global Last Subject Last End of Treatment in Q4 2023)

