5. STATISTICAL ANALYSES

5.1. General Considerations

5.1.1. Analysis Periods

5.1.1.1. Extension Analysis Period

This period includes all available data collected on or after the date of first intake of ponesimod treatment in the extension study, through the extension EOS for efficacy variables, or the last treatment date in the extension study + 15 days for safety variables.

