5.4.2.3.5. Adverse events of special interest (AESIs)

For each of the AESI categories described in Section 5.4.2.2, the number and percentage of subjects with each AESI is summarized by core treatment group and preferred term for treatment-emergent AESIs. In addition, the number and percentage of subjects having any event of that category, having any serious event, any fatal event or any event leading to premature discontinuation of study drug is presented. Similarly, treatment-emergent AESIs per 100 subject-years are summarized per AESI category.

AESI are presented in dedicated listings (one for each AESI category).

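### The bradyarrhythmia AESI carries a first-dose label but has no onset limit, and no planned summary isolates onset at the first extension dose

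*SAP*

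**What the plan says.** Section 5.4.2.2.10 lists the AESI categories and refers to Appendix 8 for their definitions. Table 10 there defines "Bradyarrhythmia occurring post-first dose" by the bradyarrhythmia query plus preferred terms such as bradycardia, hypotension, syncope and procedural hypotension. Neither place gives an onset day or hour.

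Section 5.4.2.3.5 sets the output: "the number and percentage of subjects with each AESI is summarized by core treatment group and preferred term for treatment-emergent AESIs". It adds that "treatment-emergent AESIs per 100 subject-years are summarized per AESI category". For individual cases, "AESI are presented in dedicated listings (one for each AESI category").

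For the Extension Analysis Period, section 5.1.1.1 fixes the start: "This period includes all available data collected on or after the date of first intake of ponesimod treatment in the extension study". Section 5.4.2.2.2 ends the treatment-emergent window 15 days after treatment ends. On duration, section 1.2.3 says: "The treatment period consists of 240 weeks of treatment with ponesimod including a 14-day gradual up-titration beginning on Day 1". It also says: "Treatment will stop before 240 weeks if ponesimod becomes commercially available". Section 1.2.3.1 makes an exception to the 240-week limit: "except for subjects in Ukraine where the maximum treatment duration will be 288 weeks".

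The tables restricted to Day 1 onset or Day 1 measurements (sections 5.4.2.3.1, 5.4.2.3.3, 5.4.3.2.2 and 5.4.3.3.2) all concern re-initiations. Section 5.4.1.1.7 states that the first extension dose does not count as one.

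**The concern.** Every AESI category is already tabulated as treatment-emergent, yet only this one carries a timing label. If the label means any time after the first dose, it adds nothing. If it means events around the first dose, the table does not deliver that. Either way, an event that starts years into treatment would be reported under a first-dose heading.

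The subjects most affected are those who took teriflunomide in the core study. Section 5.1.5.2 says that changes in safety on switching will be investigated, and extension Day 1 is these subjects' first exposure to ponesimod. Notes 5 and 6 to Table 12 schedule hourly blood pressure and ECG for at least four hours after that dose, so the study itself treats it as needing observation. Section 5.4.2.1 leaves switchers out of the Combined Analysis Period AE summaries, so the extension tables are where their events appear. A reader who wants bradyarrhythmia incidence at first exposure has one figure with the right name and the wrong window.

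**Working it through.** **1. Length of the counting window.** The inputs are 240 weeks (section 1.2.3), 288 weeks for Ukraine (section 1.2.3.1) and the 15-day tail (section 5.4.2.2.2). With the last dose on day weeks × 7, the window is weeks × 7 + 15 days.

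- 240 × 7 + 15 = 1695 days; 1695 / 365.25 = 4.64 years.
- 288 × 7 + 15 = 2031 days; 2031 / 365.25 = 5.56 years.

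The SAP states no figure of its own to reproduce. These are nominal maxima. A last dose on the nominal visit day would give 1696 and 2032. Section 1.2.3.1 also caps Ukraine treatment at the global last end of treatment in Q4 2023. Planned-pregnancy gaps shorten the window for some subjects.

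**2. Does any planned summary isolate the first extension dose?**

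- AESI table (5.4.2.3.5): contains these events, but does not split by onset.
- AE and SAE tables by Day 1 onset (5.4.2.3.1, 5.4.2.3.3): re-initiations only, so 5.4.1.1.7 excludes the first extension dose.
- Blood pressure and ECG Day 1 tables (5.4.3.2.2, 5.4.3.3.2): both sections remark that extension Day 1 is in a strict sense a re-initiation, then limit the outputs to restarts after an interruption during the extension.
- Blood pressure and ECG incidence tables over the period (same sections): include Day 1 data without isolating it, and concern measurements, not AESIs.
- By-visit tables (5.1.4): the general visit list goes from extension baseline to Week 2.
- AESI listing (5.4.2.3.5): shows individual cases, so a hand count is possible.

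None of these is a summary of first-dose onset. Section 6.13.3.1 refers to summaries of Day 1 AEs, but the only ones planned are for re-initiations.

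**3. How the subject-year rate treats a Day 1 event.** If 1% of subjects have one Day 1 event and mean observation is T years, the contribution to the rate is 1/T per 100 subject-years.

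- T = 1695 days: 365.25 / 1695 = 0.22.
- T = 2031 days: 365.25 / 2031 = 0.18.
- T = 351 days (an assumption, 48 × 7 + 15, not in the SAP): 365.25 / 351 = 1.04.

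The same Day 1 incidence gives a rate that depends on follow-up length. This shows only why a subject-year rate suits a first-dose risk poorly. It does not estimate bias in this study.

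**4. Is the needed variable available?** Section 5.4.2.2.2 derives extension study day of onset for all treatment-emergent AEs in the period, but no table is planned by it.

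**The case against.** The best defence is that the label is loose and the analysis is not wrong. Post-first dose can mean any time after the first dose, and a table headed treatment-emergent with a subject-year rate signals a long window. The safety objectives in section 1.1.1 are long-term safety and re-initiation, and the planned Day 1 tables follow them. The study tests no hypotheses (section 2). This limits the severity. It does not rescue the label, which is empty on that reading, or meet the intention in section 5.1.5.2 to look at switchers.

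The protocol might also fix a timing for this category. That cannot be checked here, but section 5.4.2.2.10 sends the reader to Appendix 8 for the definition, and Appendix 8 gives none.

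Several stronger readings are tempting and are not supported:

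- A reader might infer that first-dose events are missed. They are not: the Extension Analysis Period starts at that dose.
- A reader might infer that bradycardia is inseparable from non-specific terms such as syncope. Section 5.4.2.3.5 reports by preferred term, so those terms have their own rows.
- A reader might infer that switchers' events appear nowhere else. They are also in the extension AE tables of section 5.4.2.3.1.
- A reader might take the short share of the window that Day 1 occupies, or the spread of rates between 351 and 1695 days, as the size of an error. Neither measures bias. The first only compares lengths of time, and the second rests on an assumed follow-up.

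**Conclusion.** The point holds as a minor one. The category has a first-dose name and no onset limit, so its Extension Analysis Period figures cover every treatment-emergent event, nominally up to 1695 days or, for Ukraine subjects, 2031 days. No planned summary gives onset at the first extension dose; only the listing does, by hand count.

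The reported percentage cannot be lower than first-dose incidence, because it includes first-dose events. How far it exceeds that incidence cannot be estimated, because the SAP gives no event rates. The conclusion rests on the text of Table 10 and section 5.4.2.3.5 and assumes that no timing rule for this category exists outside the SAP.

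**What to change.** In section 5.4.2.3.5, for the Extension Analysis Period by core treatment group:

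- Keep the treatment-emergent total for this category, as n (%) and per 100 subject-years, and remove the first-dose wording from its label in Table 10 and section 5.4.2.2.10.
- Add one row for onset on extension Day 1 at or after the first dose, as n (%) of subjects dosed, with no subject-year rate.
- Exclude from that row any AE whose onset date was missing or partial. Section 6.13.3.1 imputes some of these to the first-dose date but already says they are not Day 1 events.
- Optionally, add a row for onset on Day 1 of a re-initiation, as n (%) of subjects who re-initiated.

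The cost is SAP wording, one or two table rows, and one flag to keep imputed dates out, because the derived onset day alone would let them in. No new data are needed. The drawback is small counts in the added rows.

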6.9. Appendix 9 Medications of Special Interest

No concomitant medications of special interest are defined.

6.10. Appendix 10 Thresholds for marked laboratory abnormalities

Table 11: Thresholds for marked laboratory abnormalities

Parameter (SI unit)	LL	LLL	НН	ннн	
Hemoglobin (g/L)	< 100	< 80	> 20 g/L above ULN (for	> 40 g/L above ULN (for pre-	
			pre-treatment assessments, and post-treatment	treatment assessments, and post- treatment assessments when	
			assessments when baseline	baseline ≤ ULN) or	
			≤ ULN) or	increase from baseline > 40 g/L	
			increase from baseline > 20	(for post-treatment assessments	
			g/L (for post-treatment	when baseline is > ULN)	
			assessments when baseline is > ULN)		
Hematocrit (L/L)	< 0.28	< 0.20	> 0.55 (female)	> 0.65	
	(female)		> 0.60 (male)		
	< 0.32 (male)				
Platelet count (10 ⁹ /L)	< 75	< 50	> 600	> 999	
WBC count (10 ⁹ /L)	NA	< 1.9	> 20.0	> 100.0	
Lymphocyte (10 ⁹ /L)	ND	< 0.2	> 4.0	≥ 8	
Neutrophils (10 ⁹ /L)	< 1.5	< 1.0	ND	ND	
Eosinophils (10 ⁹ /L)	ND	ND	> 5.0	ND	
Polymorphonuclear leucocyte/Band cells (%)	ND	ND	> 90%	> 95%	
AST (U/L)*	ND	ND	≥ 3 ULN	≥5 ULN	
ALT (U/L)*	ND	ND	≥3 ULN	≥ 5 ULN	
Total bilirubin (umol/L)	ND	ND	≥2 ULN	≥5 ULN	
			ALERT:		
			\geq 2 ULN combined with ALT or AST \geq 3 ULN		
Alkaline Phosphatase (U/L)	ND	ND	> 2.5 ULN	> 5 ULN	
INR*	ND	ND	> 1.5 ULN	> 2.5 ULN	
			ALERT:		
			\geq 1.5 combined with ALT		
			or AST \geq 3 ULN		
Creatinine (umol/L)*	ND	ND	>1.5 ULN or >1.5 × baseline	> 3 ULN or >3 × baseline	
Creatinine clearance (mL/min)	< 60	< 30	ND	ND	
Urea (mmol/L)	ND	ND	> 2.5 ULN	> 5 ULN	
Urea Nitrogen (mmol/L)	ND	ND	> 2.5 ULN	> 5 ULN	
Urate (umol/L)	ND	ND	> 1 ULN	ND	
Albumin (g/L)	< 30	< 20	ND	ND	
Glucose (mmol/L)	< 3.0	< 2.2	> 8.9	>13.9	
Potassium (mmol/L)	< 3.2	< 3.0	> 5.5	> 6.0	
Sodium (mmol/L)	ND	< 130	> 150	> 155	
Calcium (mmol/L)	< 2.0	< 1.75	> 2.9	> 3.1	
Chloride (mmol/L)	ND	ND	ND	ND	
Triglyceride (mmol/L)	ND	ND	> 3.42	> 11.4	

CONFIDENTIAL – FOIA Exemptions Apply in U.S.

Parameter (SI unit)	LL	LLL	НН	ННН
Cholesterol (mmol/L)	ND	ND	> 7.75	> 12.92
Serum pregnancy test	ND	ND	ND	Positive
Teriflunomide (ng/mL)	ND	ND	ND	> 20

^{*} HH and HHH based on CTCAE 2010 v4.03 [CTCAE 2010]. An ALERT will be sent when INR > 1.5 based on the guidance for monitoring liver test abnormalities from FDA [FDA 2009].

ALERT = study-specific alerts that trigger specific actions by the investigator [see protocol Section 5.1.12]; ALT = alanine aminotransferase; AST = aspartate aminotransferase; ND = not defined; may be complemented by definitions provided by the central laboratory (see central laboratory manual); ULN = upper limit of normal.

6.11. Appendix 11 Covid-19

This appendix describes the analyses and presentation of immunogenicity and clinical endpoints for objectives related to the assessment of immune response to Covid-19 vaccination in subjects in the AC-058B303 study.

Specific objectives are:

- To describe binding antibody concentrations to SARS-CoV-2 S protein as measured by ELISA
- To describe binding antibody concentrations to SARS-CoV-2 N protein as measured by ELISA
- To describe Covid-19 infection Adverse events (AEs).

6.11.1. Immunogenicity Variables

For Covid-19 vaccination, the following humoral immune responses are measured, including titers of neutralizing antibodies and S- and N-ELISA titers.

Humoral Assay	Purpose
SARS-CoV-2 binding antibodies to S protein	Analysis of antibodies binding to SARS-
(ELISA)	CoV-2 S protein
SARS-CoV-2 seroconversion based on	Analysis of antibodies binding to SARS-
antibodies to N protein (ELISA)	CoV-2 N protein

6.11.2. Analysis of Immunogenicity Related to Covid-19 Vaccination:

6.11.2.1. Analysis related definitions:

Covid-19 vaccine analysis set: Study subjects who have a complete Covid-19 first vaccine regimen and at least one non-zero vaccine-specific antibody titers assessed within a timeframe (defined as any timepoint prior to the start of Covid-19 vaccine or within the 365 days after the 1st dosing or within 365 days after any boosters).

First Vaccine Regimen: For each subject, the 1st and 2nd doses of vaccine in the SDTM CM dataset are considered. Definition of 1st Vaccine Regimen for Janssen vaccine: Only the 1st dose is considered.

First Booster: The 1st subsequent dose of vaccine after first vaccine regimen is considered as the First Booster.

Second Booster: The 2nd subsequent dose of vaccine after first vaccine regimen is considered as the Second Booster.

Lymphocyte counts for a subject corresponding to a specific vaccination will be determined as the minimum of the last two available values within six months prior to the first vaccination date of first vaccine regimen. If only one value is available within this range, this value will be used. If none are available in the range, the lymphocyte value corresponding to the particular vaccination will be considered missing. Categories of "Lymphocyte Count < 500 mm³" and "Lymphocyte Count >= 500 mm³" will be used in the analysis.

Analysis based on BAU/ml: In order to calibrate across different assays, the WHO has proposed International Standards (WHO IS). The WHO IS assigned unit for quantifying immunoglobulins

is BAU/ml. Per Nexelis, the conversion of ELISA units (EU/ml) to BAU/ml is as shown below (see Attachment below):

Human SARS-CoV-2 Pre-Spike IgG ELISA

The results generated for the Human SARS-CoV-2 PreSpike IgG ELISA are reported with concentration units in "ELU/mL". When required, a correlation factor of 1/7.9815 [2] will be applied to convert the reported results from ELU/mL to BAU/mL. For example, a sample with reported anti-PreSpike IgG antibody concentration of 7981.5 ELU/mL will have a concentration equivalent to 1000 BAU/mL.

The following formula may be used for converting concentration units from ELU/mL to BAU/mL:

Result (BAU/mL) = Result (ELU/mL) / 7.9815

Human SARS-CoV-2 Nucleocapsid IgG ELISA

The results generated for the Human SARS-CoV-2 Nucleocapsid IgG ELISA are reported with concentration units in "ELU/mL". When required, a correlation factor of 1/10.3383 [3] will be applied to convert the reported results from ELU/mL to BAU/mL. For example, a sample with reported anti-Nucleocapsid IgG antibody concentration of 10338.3 ELU/mL will have a concentration equivalent to 1000 BAU/mL.

The following formula may be used for converting concentration units from ELU/mL to BAU/mL:

Result (BAU/mL) = Result (ELU/mL) / 10.3383

Antibodies assessment related to vaccine sequence:

Pre-vaccine antibodies assessment: for each subject, the antibodies assessment which is prior to and closest start date of 1st vaccine regimen, is considered as Pre-vaccine antibodies assessment. Antibodies assessment post 1st vaccine regimen: for each subject, the antibody assessments on or after start of first vaccine regimen and before 1st booster are considered as antibody assessments post-1st vaccine regimen. The average of all values in a time frame of 365 days after the start of first vaccine regimen will be used as "Antibodies assessment post-1st vaccine regimen" in the analysis.

Antibodies assessment post 1st booster: for each subject, the antibody assessments on or after start of 1st booster and before the 2nd booster are considered as antibody assessments post-1st booster. The average of all values in a time frame of 365 days after the start of first booster will be used as the "Antibodies assessment post 1st booster" in the analysis.

Antibodies assessment post 2nd booster: for each subject, the antibody assessments on or after start of 2nd booster and before the 3rd booster are considered as antibody assessments post-2nd booster. The average of all values in a time frame of 365 days after start of second booster will be used as the "Antibodies assessment post 2nd booster" in the analysis.

Antibodies assessment post 3rd booster: for each subject, the antibody assessments on or after start of 3rd booster and before the 4th booster are considered as antibody assessments post-3rd booster. The average of all values in a time frame of 365 days after start of third booster will be used "Antibodies assessment post 3rd booster".

Prior Covid-19 infection evidence related to vaccine sequence:

If a subject encountered one or more Covid-19 infection AEs and the start date of AE is prior to or on the start date of 1st vaccine regimen, the subject is considered to have Prior Covid-19 infection evidence related to 1st vaccine regimen.

If a subject encountered one or more Covid-19 infection AEs and the start date of AE is prior to or on the date of 1st booster, the subject is considered to have Prior Covid-19 infection evidence related to 1st booster, irrespective if the start date of AE is prior to 1st vaccine regimen.

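### Covid-19 appendix: entry to the vaccine analysis set depends on a non-zero titer, and samples from the day of dose 1 onward count as post-regimen

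*SAP*

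**What the plan says.** All the rules are in SAP Appendix 11.

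- **Set entry (6.11.2.1).** A subject needs a complete first regimen and "at least one non-zero vaccine-specific antibody titers assessed within a timeframe". The timeframe is "defined as any timepoint prior to the start of Covid-19 vaccine or within the 365 days after the 1st dosing". A 365-day period following each booster is covered too.
- **First regimen (6.11.2.1).** "For each subject, the 1st and 2nd doses of vaccine in the SDTM CM dataset are considered"; for one named single-dose vaccine only the first dose counts.
- **Pre-vaccine sample.** "the antibodies assessment which is prior to and closest start date of 1st vaccine regimen". A sample drawn on the start date itself does not qualify.
- **Post-regimen samples.** "the antibody assessments on or after start of first vaccine regimen and before 1st booster are considered as antibody assessments post-1st vaccine regimen". For the analysed value, "The average of all values in a time frame of 365 days after the start of first vaccine regimen will be used".
- **Post-booster samples.** "the antibody assessments on or after start of 1st booster and before the 2nd booster are considered as antibody assessments post-1st booster". The second and third boosters follow the same pattern.
- **Use of the set.** Section 6.11.2.2 makes it the denominator of the frequency tabulations, and section 6.11.3 makes it the population of the Covid-19 infection AE table.
- **Summary statistic (6.11.2.2).** Geometric means and 95% CIs are obtained from log10-transformed values.

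Appendix 11 has no rule for zero or below-LLOQ ELISA results. The SAP's only LLOQ rule, in section 5.4.3.1.1, sets such results to the LLOQ and concerns the safety laboratory.

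**The concern.** The appendix sets out to describe the antibody response to vaccination in subjects on ponesimod. Two of its rules work against that aim.

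First, entry depends on the quantity being described. A fully vaccinated subject with measured titers that are all zero is informative about response, yet does not enter the set. That subject also leaves the Covid-19 infection AE table, which needs no titer at all.

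Second, the post-regimen label does not match the SAP's own definition of the regimen. For a two-dose vaccine the regimen is complete at dose 2, but the window opens on the day of dose 1. A sample taken just before the first injection is barred from the pre-vaccine value by its date and goes into the post-regimen average instead.

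At stake are the descriptive antibody summaries, their S-ELISA subgroup repeats and the Covid-19 AE table. These could be read as evidence on vaccine response under treatment.

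**Working it through.** The SAP states no result that depends on these rules, so there is none to reproduce. Its unit conversions do check: 7981.5 / 7.9815 = 1000 and 10338.3 / 10.3383 = 1000.

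**1. Who is removed.** Take subjects with a complete regimen and a zero post-regimen result. Let the pre-vaccine and post-booster results each be zero, non-zero or missing, which gives 3 × 3 = 9 patterns.

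| Pre-vaccine | Post-booster | In the set? |
|---|---|---|
| zero | zero | no |
| zero | missing | no |
| missing | zero | no |
| missing | missing | no |
| zero | non-zero | yes |
| missing | non-zero | yes |
| non-zero | zero, non-zero or missing (3 patterns) | yes |

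Four patterns are removed and five kept. The rule drops subjects with no non-zero titer anywhere in the timeframe, not every subject who failed to respond to the first regimen. In the five kept patterns the post-regimen value is still zero. Since log10(0) is undefined and no substitution is given, that value cannot enter the post-regimen geometric mean.

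**2. Possible size of the removal effect (illustration).** None of these inputs is in the SAP: geometric mean G of the subjects kept = 100, 300 or 1000 BAU/mL; floor value L given to all-zero subjects = 1 or 5 BAU/mL; share removed f = 2% to 20%.

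Geometric mean over everyone = G^(1−f) × L^f, so the overstatement factor is G / [G^(1−f) × L^f] = (G/L)^f.

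| G | L | f = 2% | 5% | 10% | 20% |
|---|---|---|---|---|---|
| 100 | 1 | 1.10 | 1.26 | 1.58 | 2.51 |
| 100 | 5 | 1.06 | 1.16 | 1.35 | 1.82 |
| 300 | 1 | 1.12 | 1.33 | 1.77 | 3.13 |
| 300 | 5 | 1.09 | 1.23 | 1.51 | 2.27 |
| 1000 | 1 | 1.15 | 1.41 | 2.00 | 3.98 |
| 1000 | 5 | 1.11 | 1.30 | 1.70 | 2.89 |

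If the laboratory never reports an exact zero, f = 0 and the factor is 1.

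**3. Possible size of the early-sample effect (illustration).** One pre-response sample at L is averaged, on the plain scale, with k later samples at G: (L + kG)/(k + 1). With G = 300 and L = 1:

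- k = 1: 301/2 = 150.5, or 0.50 of G
- k = 2: 601/3 = 200.3, or 0.67 of G
- k = 3: 901/4 = 225.2, or 0.75 of G

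If 10% of subjects have one early and one later sample, the group geometric mean is multiplied by about 0.5^0.1 = 0.93. If 10% have only an early sample, the multiplier is (1/300)^0.1 = 0.57.

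**4. Direction.** Step 2 pushes the geometric mean up and step 3 pushes it down. The SAP gives no count for either, so the net direction is open.

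**The case against.** The strongest reply has four parts.

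- **Zeros may never occur.** The assays are ELISAs reported as concentrations. Nothing in the SAP says the laboratory returns an exact zero. If low samples come back as a small positive number or at an LLOQ, no assessed subject is removed, and the condition works as a requirement to have a result. This stands as a limit on size. It does not rescue the wording: if an available result was meant, the text should say so.
- **Sampling is not timed to vaccination.** The schedule tables in Appendix 12 show no such sample, so a wide window with averaging is a reasonable response to untimed data. That defends the width of the window. It does not defend opening it before the regimen is complete.
- **The reach is limited.** Section 6.11.2.2 names the set as denominator only for the frequency tabulations; its use for the geometric means is implied. General AE tables use the SAF or EXTS (section 5.4.2.3.1), so no event is lost to the safety evaluation, and antibody values are also to be listed.
- **The analyses are descriptive.** Section 2 declares all analyses exploratory, and no main endpoint uses this set. This stands and lowers the severity.

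A reader might go further and infer that non-responders as a group are removed, so that response is overstated. The nine patterns show otherwise: one non-zero value before vaccination or after a booster keeps a subject in. A reader might also infer that the bias differs by lymphocyte category or vaccine type, the planned subgroups. That is conceivable, but nothing in the SAP shows it.

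**Conclusion.** Both rules are wrong as written, and the point should be fixed before these tables are produced. It is confined to the descriptive Covid-19 appendix.

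Two conclusions follow from the text alone. Entry depends on the measured outcome, so subjects with only zero titers leave the frequency denominators and the Covid-19 AE table. Samples from the day of dose 1, between doses and on booster days are counted as post-vaccination, contrary to the two-dose definition of the regimen.

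The size does not follow from the text. The 1.06- to 3.98-fold range and the multipliers 0.93 and 0.57 rest on assumed titers, floor values and shares. They show what the rules could do, not what they did. The within-subject averaging scale is also unstated; a plain average is the natural reading, and step 3 assumes it.

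**What to change.** Amend section 6.11.2.1 and the calculation paragraph of 6.11.2.2:

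1. **Set.** Complete first regimen plus at least one evaluable antibody result in the timeframe, whatever its value.
2. **Zero and below-LLOQ results.** State one substitution, applied before log10. The LLOQ itself would match section 5.4.3.1.1.
3. **Windows.** Open the post-regimen window a pre-specified interval after the last dose of the regimen, and each post-booster window a pre-specified interval after that booster. The SAP offers no basis for a particular number of days, so the sponsor should choose and justify one. Treat same-day samples as pre-dose unless a recorded time shows otherwise. Say where between-dose samples go, for example to the listing only.
4. **Averaging.** Average repeated values within subject on the log10 scale, to match the geometric mean. Make this change together with items 2 and 3. On log10, one sample at 1 and one at 300 average to √(1 × 300) = 17.3, against 150.5 on the plain scale, so early samples left in the window would weigh more.

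The cost is appendix wording and some reprogramming. The downside is that a few early samples leave the post-vaccination summaries, and a subject with only such samples has no post-regimen value.
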